9.3.3. Analysis of expansion and persistence of the adoptively-transferred TAA-specific T cells

Summary statistics such as mean \pm SD, medians and ranges will be calculated at pre- and post-infusion time points to evaluate the T cell expansion and persistence based on the immunological parameters including phenotype and T cell frequencies by ELispot and multimer studies, functional analyses (antigen-specific cytotoxicity and cytokine release) by chromium release assays and ELispot/intracellular cytokine staining, and the levels of serum cytokines.

Changes in each of the immunological parameters from pre-infusion to each time point of post-infusion will be assessed and compared using paired t-tests, or when appropriate, the Wilcoxon signed ranks test. Paired comparisons of these T cells within a patient at each time point will also be performed. These analyses will be performed in each disease group and in the overall patient group.

Plots of growth curves will be generated to graphically illustrate patterns of T-cell expansion and persistence. Longitudinal modeling techniques such as the random coefficient mixed model will be employed to model each of the repeatedly-measured T cells. These models account for variation in individual-level intercepts and slopes over the follow-up time. Thus, we will be able to model proliferation of T cells over time and estimate the magnitude of expansion or decline of T cells. Correlations between frequencies of these immunological parameters at each time point of follow-up will be assessed using measures of correlation coefficients.

Alternative strategies to analyze these immunological parameters include calculation of area under the curve over time or piecewise longitudinal models based on apparent trends from plotsof growth curves. Despite the small patient numbers, a data-dense study will be generated due to the repeat measurements on proliferation, immune function, and other parameters on each patient. The modeling strategies proposed here are amenable to these types of data but will however be considered exploratory and interpreted with caution due to limited study power. The

validity of the normality assumption on these data will be tested and appropriate transformations will be considered whenever indicated.

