2.0 OBJECTIVES

Primary endpoint

- 2.1 To determine the safety of up to 6 intravenous infusions of multiTAA-specific T cells in pancreatic cancer patients with metastatic, locally advanced unresectable, or resectable disease.
- 2.2 To determine the feasibility of completing a total of 6 intravenous infusions of multiTAA-specific T cells to pancreatic cancer patients with metastatic, locally advanced unresectable, or resectable disease.

Secondary endpoint

- 2.3 To evaluate the progression-free and overall survival of patients after multiTAA-specific T cell infusions

Tertiary endpoints

- 2.4 To obtain information on the expansion, persistence and anti-tumor effects of the adoptively-transferred TAA-specific T cells
- 2.5 To determine whether multiTAA-specific T cell infusion enables recruitment of the patients' endogenous immune system as measured by epitope/antigen spreading

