3.4 Targeting lymphoma, myeloma and solid tumors using tumor-targeted T cells

To use an adoptive immunotherapeutic approach to treat patients with hematologic malignancies (lymphoma and multiple myeloma) and solid tumors we developed a protocol for the in vitro generation of T cell lines targeting the TAAs Survivin, PRAME, MAGE-A4, NY-ESO-1 and SSX2, which are expressed in a range of tumors. The multi-antigen-targeted (multiTAA) T cells were generated using dendritic cells (DCs) loaded with pepmixes (overlapping peptide libraries) spanning the 5 target antigens.

Lymphoma: To date, 20 patients with lymphoma have been infused with multiTAA T cells without adverse events. Nine patients were treated for active disease. Of these, 2 patients had transient disease stabilization (5mo), 2 patients have stable disease (3mo ongoing), and 5 patients (3 HL, 1 DLBCL, 1 composite lymphoma) achieved durable complete remissions by PET, without additional therapies. These clinical responses correlated with a progressive increase in the frequency of tumor-specific T cells directed against both targeted and non-targeted TAAs, indicating that the infused T cells induced localized in vivo inflammation, resulting in endogenous T cell activation and antigen/epitope spreading. A further 11 patients were infused as adjuvant therapy. Of these, all but 2 remain in remission (median 17 months postinfusion, range 6-34 months) - a benefit likely due to the infused cells as the best prior response in these patients produced remissions lasting a median of only 4 months (range 1-6 months). These data support both the safety and clinical benefit of autologous multiTAA T cells as adjuvant therapy for lymphoma patients.

Myeloma and solid tumors: We subsequently extended this approach to other malignancies and to date we have infused 7 patients with multiple myeloma and 5 patients with solid tumors (1 squamous cell carcinoma, 1 lung cancer, and 3 osteosarcoma) with a similar safety.

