5.1 Blood procurement for multiTAA T cell and APC generation

Generation of multiTAA T cells requires the generation of several different components from peripheral blood mononuclear cells (PBMC). The line will be derived from patient PBMCs, by stimulation with antigen presenting cells (APCs) pulsed with pepmixes spanning the TAAs SSX2, MAGEA4, Survivin, PRAME, and NY-ESO-1. The initial stimulation will be performed in the presence of the Th1/pro-proliferative cytokines interleukin (IL) 7, IL12, IL15, and IL6 and cells will be expanded in the presence of IL2 or IL15. The APCs used to stimulate and expand the tumor-specific T cells will be DCs derived from patient mononuclear cells.

For T cell generation, we will collect either:

- * a unit of blood (~450ml) (for patients with ALC of >500) or
- * a maximum blood draw of 450 ml peripheral blood obtained in 1-3 draws over a two month period for CTL generation, testing for infectious viruses and HLA typing. PBMCs will be separated from whole blood using ficoll gradients. T cells and monocyte-derived dendritic cells (DCs) can be prepared from fresh or cryopreserved PBMC.

To initiate multiTAA T cells we will make DCs by culture of PBMC-derived monocytes with cytokines (GM-CSF, IL-4) followed by maturation with a standard DC maturation cocktail (IL-1 β , IL6, TNF α and PGE1). These mature DCs will be pulsed for 30-60 mins with a mastermix of pepmixes spanning the target antigens PRAME, SSX2, MAGEA4, NY-ESO-1 and Survivin. For dilution 1ul of each pepmix (200ng/peptide) will be added to 200ul Cell Genix/RPMI media and 50-100ul will be used to pulse the DCs ($\leq 5 \times 10^6$ DCs - 50ul; $> 5 \times 10^6$ DCs - 100ul). Subsequently the DCs will be washed once and used to stimulate PBMC-derived T cells in the presence of a T cell activating cocktail, IL7, IL15, IL12 and IL6 at a responder:stimulator ratio of at least 10:1. For initiation, DCs will be prepared from peripheral blood and the T cells will be derived from the monocyte-depleted PBMC fraction.

To expand the tumor-specific T cells we will use pepmix-pulsed DCs for the second and subsequent stimulations and cells will be cultured in the presence of IL2 or IL15.

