At the end of the culture period, multiTAA T cells will be cryopreserved and aliquots tested for phenotype, function, specificity, identity and sterility. The frequency of tumor-specific T cells will be determined using intracellular cytokine staining, ELISPOT assay, and/or HLA multimers, if available. Effector memory phenotype and T cell subsets will be analyzed by flow cytometry.

Products that meet study specific release criteria, as detailed on the COA, will be infused as per Section 5.2.

If a positive sterility testing result is reported after the product is infused, the FDA and other relevant parties will be notified as per manufacturing SOP B01.03.XX (Product Quality Assurance Program and Release and Return of Clinical GMP/GTP Products) and clinical research SOP J02.06.XX (Serious Adverse Experience and Unanticipated Problem Reporting). Our management of such a situation is further described in our SOP F05.09.XX (Management of CulturePositive Cell Therapy Products).

We will use pepmixes produced by JPT Technologies as an antigen source. These pepmixes are overlapping peptide libraries (15 mers overlapping by 11 amino acids) spanning the entire sequence of each of the antigens of interest as per our lymphoma (TACTAL), myeloma (TACTAM), and solid tumor (TACTASOM) studies.

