5.2 Administration and Monitoring

Three disease groups will be studied.

Group A: Patients with locally advanced or metastatic adenocarcinoma who are responding (defined as stable disease or tumor volume reduction) following 3 cycles of first line chemotherapy will be evaluated in the clinic and receive 6 infusions with a fixed dose of multiTAA T cells starting on chemotherapy cycle 4 and occurring on the 4th week of the cycle, which is a chemotherapy “off” week.

Group B: Patients with locally advanced or metastatic adenocarcinoma who have failed first line chemotherapy or are intolerant or ineligible to receive standard of care chemotherapy will be evaluated in the clinic and receive 6 infusions (administered at monthly intervals) with a fixed dose of multiTAA T cells.

Group C: Patients with resectable pancreatic adenocarcinoma following completion of neoadjuvant chemotherapy, radiotherapy or combination. These patients will receive 6 infusions with a fixed dose of multiTAA T cells. One infusion will occur 4 weeks prior to surgical resection (with an option to infuse up to one week earlier) and after the completion of all pre-operative chemotherapy and/or radiation. The subsequent 5 infusions will occur at monthly intervals beginning 8 weeks post-surgery.

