7.0 PATIENT EVALUATION

7.1 Follow-up Interval

Patients shall be seen in clinic prior to each T cell infusion and evaluated (seen in clinic or contacted by research coordinator) at 1 and 2 weeks after each infusion, week 4, 6, and 8 after the last infusion and then at 3, 6, 9 and 12 months after the last infusion. Study-related blood draws will cease 12 months after the last T cell infusion but we will then continue to follow patients clinically for up to 4 additional years (total of 5 years follow-up) to evaluate long-term disease responses. If persistence of cells is noted at the 12 month visit, additional follow up will be added. Additional visits will be obtained as clinically indicated.

- 7.2 A complete history and physical examination is necessary prior to administration of multiTAA T cells. Medical history will be obtained at every follow-up visit and will be reviewed annually for 5 years.

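### The planned assays describe circulating antigen-specific T-cell frequency but cannot credit it to the infused autologous cells, and early changes in Group A (and part of Group C) are likely confounded with chemotherapy phase

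*Combined protocol and SAP*

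**What the plan says.** Objective 2.4 (tertiary) is "To obtain information on the expansion, persistence and anti-tumor effects of the adoptively-transferred TAA-specific T cells". Objective 2.5 (also tertiary) asks whether the infusion "enables recruitment of the patients' endogenous immune system as measured by epitope/antigen spreading".

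On the product, section 5.1 states: "The line will be derived from patient PBMCs, by stimulation with antigen presenting cells (APCs) pulsed with pepmixes". The pepmixes are peptide libraries "spanning the entire sequence of each of the antigens of interest". Section 5.1 describes no gene mark or other tag.

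On measurement, section 7.3.4 lists multimer analysis, ELISpot, intracellular cytokine staining and cytotoxicity assays, with serum cytokines. Section 9.3.3, whose title refers to the transferred cells, uses these to "evaluate the T cell expansion and persistence based on the immunological parameters including phenotype and T cell frequencies by ELispot and multimer studies". It tests each post-infusion time point against pre-infusion with paired tests, per disease group and overall, and adds a random-coefficient mixed model. It names no term for chemotherapy phase. It calls the modelling exploratory, giving limited power as the reason.

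The word persistence also affects conduct. Section 7.1 says: "If persistence of cells is noted at the 12 month visit, additional follow up will be added".

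On timing, section 5.2 has Group A infused "starting on chemotherapy cycle 4 and occurring on the 4th week of the cycle", an off week. Section 4.3.10 requires a washout from conventional therapy for Groups B and C only. The section 7.4 calendar marks standard-of-care (SOC) weeks for Groups A and C and has no such row for Group B.

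**The concern.** There are two separate sources of bias, and a larger sample would remove neither.

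**Origin.** An assay that counts T cells by specificity adds infused and endogenous cells together. Section 3.4 reports that in lymphoma, T cells rose against targeted and non-targeted antigens alike, and reads this as local inflammation "resulting in endogenous T cell activation and antigen/epitope spreading". If the same happens here, endogenous recruitment against the five antigens would be reported as expansion or persistence of the product, and could prompt the extra follow-up in section 7.1.

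**Chemotherapy phase.** If the baseline is drawn in an off week and the early post-infusion samples in treatment weeks, the paired change mixes T-cell kinetics with any effect of chemotherapy on T-cell counts or function. Section 9.3.3 also analyses the overall group, which puts these changes together with Group B, where the calendar shows no such weeks.

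At stake is the mechanistic conclusion: whether the trial may say that the infused cells expanded and lasted.

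**Working it through.** The plan states no figure for objective 2.4, so there is none to reproduce. The check has four parts.

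**1. What the assays identify.** Set sections 5.1, 7.3.4 and 9.3.3 side by side. The product is autologous and unmarked, and it is raised against whole-antigen libraries. The blood assays read antigen specificity or function. An endogenous T cell against one of the five antigens scores the same as an infused one. No clonotype comparison between product and blood is described. Frequency is therefore measured, but origin is not.

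**2. Calendar count (section 7.4, post-infusion immune-function rows against SOC weeks).**

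| Group and window | Immune samples | In SOC weeks | Not in SOC weeks |
|---|---|---|---|
| A, weeks 1–22 | 17 | 12 (weeks 1, 2, 5, 6, 9, 10, 13, 14, 17, 18, 21, 22) | 5 (weeks 4, 8, 12, 16, 20) |
| A, with follow-up | 17 + 7 = 24 | 12 | 5, plus 7 with no phase assigned |
| C, weeks 1–18 after infusion 2 | 14 | 6 (weeks 1, 2, 5, 6, 9, 10) | 8 |

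The 7 follow-up samples are weeks 4, 6 and 8 and months 3, 6, 9 and 12 after the last infusion. The Group A shares are 12/17 = 71% and 12/24 = 50%. Phase-matched contrasts through week 22 are 5/17 = 29%. Group A is at most 15/45 = 33% of the pooled sample (section 9.1).

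**3. What a phase shift alone could do (illustration).** Assume no true expansion, n = 15, and a pure phase effect of d standard deviations of the within-patient difference. The chance of a significant two-sided 5% paired t-test is P(|T| > 2.145), where T is noncentral t with 14 degrees of freedom and noncentrality d√15 = 3.873d.

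| d (assumed) | Noncentrality | Chance of a significant change |
|---|---|---|
| 0 | 0 | 5.0% |
| 0.25 | 0.97 | 14.7% |
| 0.5 | 1.94 | 43.8% |
| 0.75 | 2.90 | 77.1% |

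The documents give no value or sign for d. A shift in the other direction would hide a real rise instead.

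**4. Whether a phase term can be estimated.** In Group A through week 22, every sample 1–2 weeks after an infusion is in an SOC week, and every sample at 4 weeks is not. Within Group A alone, phase and time since infusion therefore coincide, and a phase term would absorb a true early peak. Information to separate them comes from Group B, and from Group C weeks 13, 14, 17 and 18. On the monthly schedule those are also 1–2 weeks after an infusion, but carry no SOC mark.

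**The case against.** The case on the other side is substantial, and much of it limits the point.

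- A reader might infer that objective 2.4 cannot be answered. The documents do not support that. It is tertiary, asks only for information, and includes anti-tumor effects, which section 9.3.2 analyses separately. Circulating frequency remains describable; only attribution fails.
- A reader might infer that objectives 2.4 and 2.5 cannot be told apart. Responses to antigens outside the five can be called endogenous. Section 5.1 also has each product tested for specificity, so a rise against an antigen the product did not recognise is probably endogenous. Partial attribution is possible.
- Section 7.3.4 lists its assays as examples and section 9.3.3 names no antigens, so silence does not show that non-targeted antigens are excluded. What stands is that section 9.3 names no analysis for objective 2.5. That is mostly missing detail.
- Counting only weeks 1–2 after each Group A infusion would give 12 of 12 samples in SOC weeks. That leaves out five off-week samples and seven follow-up samples. Late persistence rests largely on the latter, so the timing problem mainly concerns early expansion.
- The calendar says SOC, not chemotherapy, and does not date the pre-infusion draw to a cycle week. The off-week baseline is inferred from section 5.2: likely, not stated. After three prior cycles it is not a chemotherapy-free baseline either.
- Per-group results and the off-week contrasts are already within the section 9.3.3 plan. Making only those the main comparison would discard the early window, and samples from week 8 on follow repeated infusions.

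The exploratory caveat does not answer the point, because it cites power, and both problems are bias.

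**Conclusion.** The point holds in a limited form. For the five targeted antigens, the planned assays give the frequency of infused plus endogenous cells. They cannot support a statement that the infused cells expanded or persisted. This rests on the absence of any described marker or clonotype comparison and on the protocol's own expectation of endogenous activation.

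The early pre-to-post changes are likely confounded with chemotherapy phase at 12 of 17 Group A time points through week 22 (12 of 24 over the full calendar) and at 6 of 14 Group C time points after infusion 2. This assumes that SOC weeks in the calendar are chemotherapy weeks and, for Group A, that the pre-infusion sample falls in the off week. Size and direction are unknown, and the percentages in the illustration depend wholly on an assumed shift.

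The primary safety and feasibility endpoints are unaffected.

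**What to change.** 1. In 2.4, 7.1 and 9.3.3, relabel the endpoint as *change in circulating TAA-specific T-cell frequency (infused plus endogenous)*. Limit claims that infused cells persisted to patients with product-to-blood evidence, such as shared clonotypes, if that is obtained.
2. In the planned mixed model, add chemotherapy phase (SOC week versus off week) as a time-varying term for Groups A and C. Fit the groups jointly, and state the assumption that the time course after an infusion is shared, since Group A alone cannot separate the two.
3. Report the phase-matched Group A contrasts (pre-infusion against weeks 4, 8, 12, 16 and 20) alongside the week 1–2 contrasts, not in their place. Do not interpret pooled week 1–2 changes across groups without the phase adjustment.
4. For objective 2.5, name an analysis that reads spreading from responses to antigens outside the five, at pre-infusion and the same later time points, where cell yield permits.

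Cost: items 1 and 3 are wording and reporting. Item 2 adds one model term in a small sample. Item 4 needs extra assay wells from draws of 20–40 ml, which section 7.3.7 reduces when hemoglobin is below 7.0 g/dl, so some patients may lack enough cells. The trial ends with a weaker claim than persistence of the infused cells, but one its data can support.

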9.3.4. Analysis of Laboratory Data

Laboratory data, which includes CBC, BUN, creatinine, and liver function tests, will be examined in different ways. Descriptive statistics (means, standard deviations, medians and ranges) at pre-infusion, at weeks 1, 2, 4, 6, 8 and at months 3, 6, 9, and 12 post- T cell infusion will be calculated and summarized. A scatter diagram depicting laboratory values at each time point for each patient will also be generated. To analyze changes in laboratory values, a shift table with Stuart-Maxwell chi-square analysis of the change in the normal range from pre-infusion to post infusion time points (using high, normal, low) will be performed. When appropriate, these tables will be collapsed and the McNemar's test applied in place of the Stuart-Maxwell test. Diagnostic imaging (CT scans, MRI, nuclear imaging) and/or blood tests (serum cytokines) will be also summarized and plotted. These statistical analyses will be performed for each disease group and the overall patient group.

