4.3.3 Patients with life expectancy ≥ 12 weeks

4.3.4 Age ≥ 18

4.3.5 Pulse oximetry of $>95\%$ on room air in patients who previously received radiation therapy

4.3.6 Patients with an ECOG score of ≤ 2 or Karnofsky score of ≥ 50 as described below:

ECOG Performance Status	
Grade	ECOG
0	Full active, able to carry on all pre-disease performance without restriction
1	Restricted in physically strenuous activity but ambulatory and able to carry out work of a light or sedentary nature, e.g., light house work, office work
2	Ambulatory and capable of all selfcare but unable to carry out any work activities. Up and more than 50% of waking hours
3	Capable of only limited selfcare, confined to bed or chair more than 50% of waking hours
4	Completely disabled. Cannot carry on any selfcare. Totally confined to bed or chair
5	Dead

Performance Status Criteria	
Karnofsky performance scores are intended to be multiples of 10	
Karnofsky	Description
Score	Description
100	Normal, no complaints, no evidence of disease

90	Able to carry on normal activity, minor signs or symptoms of disease
80	Normal activity with effort; some signs or symptoms of disease.
70	Cares for self, unable to carry on normal activity or do active work.
60	Required occasional assistance, but is able to care for most of his/her needs.
50	Requires considerable assistance and frequent medical care.
40	Disabled, requires special care and assistance.
30	Severely disabled, hospitalization indicated. Death not imminent.
20	Very sick, hospitalization indicated. Death not imminent.
10	Moribund, fatal processes progressing rapidly.

- 4.3.7 Patients with bilirubin $\leq 2x$ upper limit of normal, AST $\leq 3x$ upper limit of normal, Hgb ≥ 7.0 g/dl (transfusion allowed).
- 4.3.8 Patients with a creatinine $\leq 2x$ upper limit of normal for age
- 4.3.9 Patients should have been off other investigational therapy for one month prior to receiving treatment on this study.
- 4.3.10 For Groups B or C patients must be off conventional therapy for at least 1 week prior to receiving treatment on this study.
- 4.3.11 Informed Consent explained to, understood by and signed by patient. Patient given copy of informed consent.

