9.2 Sample Size Determination and Trial Monitoring

In each of the disease groups, the primary goals are to study the safety of multiTAA-specific T cells and determine the feasibility of administering 6 infusions of cells.

To assess the safety of multiTAA-specific T cells: The sample size is 15 patients in each disease group, calculated based on the considerations as follows. To study whether there are excessive treatment-related serious adverse events (tSAE), a tSAE rate of 20% is considered excessive (corresponding to the alternative hypothesis), while a rate below 20% is considered acceptable. Based on our previous experience with T cell therapy, we anticipate at most 1.5% rate (corresponding to the null hypothesis). The monitoring rule is that if more than one tSAE is observed, then the treatment is considered unsafe and the accrual to the trial will be halted for that disease group.

Under the alternative hypothesis that the true tSAE rate is 20%, then the probability of observing more than one tSAE event out of 15 patients is 83.3% (statistical power for rejecting the null hypothesis, based on the exact binomial distribution). Under the null hypothesis that the true tSAE rate is 1.5%, the probability of observing more than one tSAE event out of 15 patients is only 2.08% (type I error for rejecting the null hypothesis, based on the binomial distribution).

There will be no formal interim analysis of safety but we will employ an ad hoc monitoring rule. The cumulative number of treatment-related serious adverse events will be counted for every 3 patients within each group. If there is more than 1 tSAE within a group, then the accrual to that group will be halted for excessive treatment-related serious adverse events. We will be looking at the data for at most 5 times for each group. Under the null hypothesis that the true tSAE rate is 1.5%, the probability of observing more than one tSAE event out of every 3, 6, 9, 12 and 15 patients is 0.07%, 0.32%, 0.76%, 1.34% and 2.08%, respectively. The overall type I error is thus controlled at 4.57% level.

The total sample size is 45. If there is any death deemed possibly or probably related to multiTAA T cell infusion, the study will halt patient accrual for the respective disease group, and the data will undergo a thorough internal review and the outcome discussed with the FDA.

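### The three-class laboratory shift table in 9.3.4 cannot register further worsening in patients who enter already abnormal, and its per-group test is weak at 15 patients

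*Combined protocol and SAP*

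**What the plan says.** Section 9.3.4 covers blood counts, BUN, creatinine and liver function tests, which "will be examined in different ways". Three displays are planned:

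- Summary statistics: "Descriptive statistics (means, standard deviations, medians and ranges) at pre-infusion, at weeks 1, 2, 4, 6, 8 and at months 3, 6, 9, and 12" after infusion.
- Individual values: "A scatter diagram depicting laboratory values at each time point for each patient will also be generated".
- For change from baseline, a shift table with "Stuart-Maxwell chi-square analysis of the change in the normal range from pre-infusion to post infusion time points (using high, normal, low". The fallback reads: "When appropriate, these tables will be collapsed and the McNemar's test applied in place of the Stuart-Maxwell test".

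On the level of analysis: "These statistical analyses will be performed for each disease group and the overall patient group". Under 9.1 and 9.2 that is up to 15 patients per group and 45 in all.

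The section states no significance level, no version of either test and no power. Section 9.3.3 calls its own models exploratory because of limited power; 9.3.4 carries no such caution.

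The entry criteria allow values outside the normal range. Section 4.3.7 accepts "Patients with bilirubin $\leq 2x$ upper limit of normal, AST $\leq 3x$ upper limit of normal", and hemoglobin down to 7.0 g/dl with transfusion allowed. Section 4.3.8 accepts creatinine up to twice the upper limit.

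**The concern.** The shift table and its test are the only formal analysis of laboratory change in the section. They have one class above the normal range and one below it. A patient who starts in an outer class and moves further out does not leave it, and the entry criteria make such patients likely.

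The tests also compare opposing movements, so recovery in some patients offsets worsening in others. In a group of 15, few patients are left to drive the result.

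What is at stake is how the output reads. Safety is a primary objective (2.1). A per-group table with nothing off the diagonal and a non-significant p-value could be taken as reassurance, although it says nothing about deterioration within the outer classes and little about shifts of moderate frequency.

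**Working it through.** **1. What the table and tests can register.** Let b be the number of patients moving one way between two classes (say normal to high) and c the number moving back. McNemar's statistic is (b − c)²/(b + c). Stuart-Maxwell uses the differences between the baseline and follow-up class totals, with variances built from the off-diagonal cells. Patients on the diagonal drop out of both. As an illustration, a patient who enters with AST at 2.5 times the upper limit (the entry limit is 3 times) and rises to 10 times is high before and high after. Neither b nor c changes.

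**2. The plan's own power figures (9.2).** These concern treatment-related serious adverse events, with more than one event in 15 as the trigger.
- At 20%: 1 − 0.8¹⁵ − 15 × 0.2 × 0.8¹⁴ = 83.29% (stated 83.3%).
- At 1.5%: 1 − 0.985¹⁵ − 15 × 0.015 × 0.985¹⁴ = 2.08% (stated 2.08%).

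Both reproduce. No counterpart is given for the laboratory tests.

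**3. Inputs for the laboratory test.** From the plan: n = 15 per group and 45 overall. Assumed here: 20% of patients shift one way, nobody shifts back, all start normal, two-sided level 0.05. The 20% is borrowed as a benchmark. In 9.2 "a tSAE rate of 20% is considered excessive", and that rate is for related serious events, not for leaving a normal range.

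**4. One-way shifts needed for p ≤ 0.05 (c = 0).**

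| Version | p-value formula | Last non-significant b | First significant b |
|---|---|---|---|
| Exact McNemar | 2 × 0.5ᵇ | 5 (0.0625) | 6 (0.031) |
| Continuity-corrected McNemar | (b − 1)²/b on 1 df | 5 (0.074) | 6 (0.041) |
| Stuart-Maxwell, 2 df | b on 2 df | 5 (0.082) | 6 (0.0498) |
| Uncorrected McNemar, or Stuart-Maxwell reduced to 1 df | b on 1 df | 3 (0.083) | 4 (0.0455) |

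The uncorrected version rejects at b = 4, where the exact two-sided p-value is 2 × 0.5⁴ = 0.125.

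**5. Power with no reverse shifts.** With c = 0, power is the binomial probability of reaching the critical count.
- n = 15: P(X ≥ 6) = 6.1%; P(X ≥ 4) = 35.2%.
- n = 45: P(X ≥ 6) = 91.0%; P(X ≥ 4) = 98.7%.

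**6. Sensitivity.** If 5% also shift back (assumed), sum the trinomial probabilities of all (b, c) pairs that give p ≤ 0.05.

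| n | Exact McNemar | Continuity-corrected | Uncorrected |
|---|---|---|---|
| 15 | 3.6% | 3.6% | 18.8% |
| 45 | 42.2% | 41.8% | 52.3% |

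If only 10 of 15 patients start normal (assumed), with no reverse shifts: P(X ≥ 6) = 0.6% and P(X ≥ 4) = 12.1%.

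**The case against.** The strongest reply is that the shift table is one display among several. Individual values are plotted for every patient and the ranges are reported, so a large rise from an abnormal baseline can be seen. Toxicity is graded by CTCAE, with severity tables and per-patient listings (9.3.1, 12.3.1). Accrual is governed by the serious-event rule, which has 83.3% power at 20%. No decision rests on the laboratory p-values, and the analysis is also run on all patients, where power is far higher.

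Much of this stands, and it rules out three stronger readings that a reader might infer:

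- That the laboratory analysis as a whole cannot show worsening from an abnormal baseline. The scatter diagrams and ranges use actual values, so the limitation belongs to the table and its test.
- That the test has 6% power at a rate the plan itself calls excessive for laboratory shifts. The plan sets no such rate, and 6% is only one end of a range that depends on the test version.
- That safety monitoring is compromised. The accrual rule does not use this test, and nothing in the documents suggests that graded laboratory toxicity would go unreported.

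The reply does not remove the point itself. Group summaries do not link a patient's baseline to that patient's worst value. Scatter diagrams supply no threshold, count or interval. The severity tables in 9.3.1 depend on an event being recorded as adverse, and the accrual rule counts only events judged related to the T cells (9.1). A table of baseline against worst grade needs neither step.

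**Conclusion.** The point holds for the shift table and its paired test. Same-direction worsening from an abnormal baseline cannot register there, by construction, and 4.3.7 and 4.3.8 admit patients to whom this applies. How many will enter in that state is not stated.

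Per group, the test would miss a 20% one-way shift about 65% to 94% of the time (100 − 35.2 and 100 − 6.1). This assumes no reverse shifts, all patients normal at entry and a two-sided 0.05 level. The spread comes from the unstated test version. The weakness is chiefly a per-group one: pooled power is 91% to 99%, although an assumed 5% of reverse shifts brings it down to 42% to 52%.

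This is a cheap improvement to a secondary safety display, not a gap in the trial's safety rules.

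**What to change.** In 9.3.4:

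1. For each analyte with a CTCAE grade, replace the three-class table with baseline grade against worst post-infusion grade, on the scale already adopted in 12.3. State the window over which the worst value is taken. Keep high/normal/low for any analyte without a grade.
2. Report, per group and overall, the number of patients who worsen by two or more grades or newly reach grade 3-4, with exact 95% binomial intervals, the method 9.3.2 already uses for response.
3. Drop the Stuart-Maxwell and McNemar p-values, or label them descriptive and name the version used.

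The intervals show plainly what a clean table can exclude. With no such patient among 15, the upper limit is 1 − 0.025^(1/15) = 21.8%; with none among 45, it is 1 − 0.025^(1/45) = 7.9%.

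The cost is revised wording and a different table program, with no new data and no change to any clinical rule. What is lost is the p-values. Grades are also classes, so worsening within a grade would still need the scatter diagrams, which should stay.
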